6.4 Concomitant Medications/Treatments

All antidopaminergic agents (including typical and atypical antipsychotics, antidopaminergic antiemetics and antidopaminergic antidepressants) are restricted during the period of this trial and would in any case be contraindicated for use in patients with Parkinson disease.

6.5 Other Modalities or Procedures

No other modalities (e.g., surgery, radiotherapy) or procedures (e.g., hematopoietic stem cell transplantation) will be used in the protocol treatment.

6.6 Duration of Therapy

In the absence of treatment delays due to adverse events, treatment may continue for a total of 24 weeks or until:

- Disease progression is documented per the judgment of the investigator
- Inter-current illness that prevents further administration of treatment
- Unacceptable adverse event(s) (see section 6.3)
- Patient decides to withdraw from the study, OR
- General or specific changes in the patient's condition render the patient unacceptable for further treatment in the judgment of the investigator.

6.7 Duration of Follow Up

Patients will be reassessed at a 2 week follow-up visit after completion of the active treatment arm to determine if there are any adverse events associated with withdrawal of Modafinil 50 mg. As subjects will be recruited from the population of patients already cared for at the UAMS movement disorders clinic they may continue to get regular clinic visits at UAMS for the treatment of their Parkinson disease as determined by the movement disorders neurologist after the study period has elapsed.

6.8 Removal of Patients from Protocol Therapy

Patients will be removed from therapy when any of the criteria listed in Section 7.4 apply. Notify the Principal Investigator, and document the reason for study removal and the date the patient was removed in the Case Report Form. The patient should be followed-up per protocol.

6.9 Patient Replacement

Subjects who have completed less than 2 weeks of the active treatment arm may be replaced with an alternative subject who would be enrolled in the same treatment arm as the subject being replaced, i.e. either the early-start or delayed-start arm. Up to 25 subjects may be recruited in order to try and obtain 20 subjects completing the study.

7.0 STUDY PROCEDURES

7.1 Screening/Baseline Procedures

Assessments performed exclusively to determine eligibility for this study will be done only after obtaining informed consent. Assessments performed for clinical indications (not

PI: [name], PhD

Sponsor: UAMS

exclusively to determine study eligibility) may be used for baseline values even if the studies were done before informed consent was obtained.

All screening procedures must be performed within 14 days prior to registration unless otherwise stated. The screening procedures include:

7.1.1 Informed Consent and HIPAA Authorization

7.1.2 Medical history

Complete medical and surgical history, and history of infections. Medical chart will be reviewed for potential contraindications to participation including available hepatic function tests, renal functions tests, and ECGs or echocardiograms if available.

7.1.3 Demographics

Age, gender, race, ethnicity

7.1.4 Review subject eligibility criteria

7.1.5 Review previous and concomitant medications

7.1.6 Physical exam including vital signs, height and weight

Vital signs (temperature, pulse, respirations, orthostatic blood pressure), height, weight

7.1.7 Adverse event assessment

Baseline adverse events will be assessed. See section 9 for Adverse Event monitoring and reporting.

7.2 Procedures During Treatment

Gait and Balance Assessments:

Subjects will be asked to walk on the 20' long by 4' wide pressure sensor-impregnated Zeno Walkway using a number of protocols as outlined below. These assessments will be formed at enrollment, 6 weeks on Modafinil, 12 weeks on Modafinil and 2 weeks after stopping Modafinil. See Table 1 below for detailed study schedule.

- 1. Walking at a comfortable pace on and off the mat, 8 lengths of the mat.
- 2. Walking at a comfortable pace on and off the mat, 8 lengths of the mat, with two dual-task paradigms
 - a. Texting on a cellular phone
 - b. Counting backwards aloud from 250
- 3. Walking at a comfortable pace making pivot turns on the mat, 8 lengths of the mat.
- Walking at a comfortable pace making U-turns turns on the mat, 8 lengths of the mat.
- 5. Sit-Stand-Walk test: starting in a sitting position, standing up, walking to the end of the mat, pivot turn, walk back and sit back down, 4 repetition.
- 6. Tandem walk the length of the mat
- 7. Postural sway: stand with feet together for 30 seconds and then with feet in tandem for 30 seconds

PI: [name], PhD

Sponsor: UAMS

8. Pull test: stand with examiner behind, pulling backwards at the shoulders at 4 different strengths twice.

- a. First time asking the subject to step back only if needed
- b. Second time asking the subject to step back every time they get pulled

Data from the Zeno Walkway will be collected using a desktop computer running the PKMAS software. The resulting data will be analyzed for standard characteristics of gait such as step time and length, stride time and length, stride velocity and acceleration, swing time, gait cycle time, center of pressure of each foot, center of body mass and coefficients of variation between these. In addition, parameters of the episodic freezing episodes such as time to overcome the freeze, center of mass variation during the freeze and amplitude and frequency of tremor in the legs during the freezing episodes will also be captured and evaluated. The program also provides raw data of every sensor reading during footfall allowing for a large number of additional parameters to be calculated and based on initial results, these parameters may be assessed in the future. The sensor data is time locked to two cameras to allow for accurate characterization of foot falls. Subjects will be assessed in the OFF levodopa state and 60 minutes after taking their regularly prescribed levodopa dose at each time point.

Additional assessments (See Table 1 below for detailed study schedule):

The following measures/scales will be performed at every visit (unless otherwise specified) by [name] (utilizing his protected clinical research time), or other study personnel:

- 1. Demographic information will be recorded at screening/first visit (5 minutes).
- 2. Complete neurological examination will be given every 12 weeks and at visit six (15 minutes).
- 3. Vital Signs (orthostatic blood pressure and heart rate, weight) (5 minutes)
- 4. Medication profile will be recorded or reviewed every visit (5 minutes).
- 5. Complete movement disorders examination at every visit (10 minutes).
- 6. Unified Parkinson's Disease Rating Scale (UPDRS) (10 minutes).
- 7. Freezing of gait questionnaire (FOG-Q) (or NFOG-Q) (2-3 minutes).
- 8. Schwab and England Activities of Daily Living scale (1 minute).
- 9. Hoehn and Yahr Scale Staging of Parkinson's disease (no additional patient time).
- 10. Epworth sleepiness scale (2-3 minutes).
- 11. REM Sleep Behavior Disorder Screening Questionnaire (2-3 minutes).
- 12. Apathy Evaluation scale (AES-S) (5 minutes).
- 13. Parkinson's disease questionnaire for quality of life (PDQ-39) (7-10 minutes).
- 14. Montreal Cognitive Assessment (MoCA) every 12 weeks and at visit six (10-15 minutes).
- 15. Frontal assessment battery (FAB) every 12 weeks and at visit six (5-10 minutes).

16

Study Title: Modafinil for FOG (UAMS IRB#206341) PI: [name], PhD

Sponsor: UAMS

- 16. Stroop test every 12 weeks and at visit six (3-5 minutes).
- 17. Scales for outcome in Parkinson's disease cognition (SCOPA-COG) every 12 weeks and at visit six (10-15 minutes).

7.3 **Schedule of Time and Events Table**

Activity	Visit 1 (Screening Visit)	Visit 2 (6 weeks)	Visit 3 (12 weeks)	Visit 4 (18 weeks)	Visit 5 (24 weeks)	Visit 6 (26 weeks)
Inclusion/Exclusion	Х					
Informed Consent Signed	Х					
HIPAA Authorization Signed	Х					
Demographic Information	Х					
Vital Signs ¹	Х	Х	Х	Х	Х	Х
Medication Profile ¹	Х	Х	Х	Х	Х	Х
Complete Neurological Examination ¹	Х		Х		Х	Х
Complete Movement Disorders Examination ¹	Х	Х	Х	Х	Х	Х
Gait and Balance Measurements ¹	Х	Х	Х	Х	Х	Х
Unified Parkinson's Disease Rating Scale (UPDRS) ¹	х	Х	х	х	х	х
Freezing of Gait Questionnaire (FOG-Q or NFOG-Q) ¹	х	Х	х	х	х	х
Schwab & England Activities of Daily Living Scale ¹	х	Х	х	х	х	Х
Hoehn & Yahr Scale Staging of Parkinson's Disease ¹	х	Х	х	х	х	Х
Montreal Cognitive Assessment (MoCA) ¹	Х		Х		Х	Х
Frontal Assessment Battery (FAB) ¹	Х		Х		Х	Х
Stroop Test ¹	Х		Х		Х	Х
Scales for Outcome in Parkinson's Disease – Cognition (SCOPA-COG)	х		х		х	х

PI: [name], PhD

Sponsor: UAMS

Epworth Sleepiness Scale ²	х	х	Х	Х	х	х
REM Sleep Behavior Disorder Screening Questionnaire ²	×	Х	x	x	×	х
Apathy Evaluation Scale (AES-S) ²	Х	х	Х	Х	Х	Х
Parkinson's Disease Questionnaire for Quality of Life (PDQ-39) ²	х	Х	х	х	х	х

¹ Study staff performed

7.4 Removal of Subjects from Study

Patients can be taken off the study treatment and/or study at any time at their own request, or they may be withdrawn at the discretion of the investigator for safety, behavioral or administrative reasons. The reason(s) for discontinuation will be documented and may include:

- Patient voluntarily withdraws from treatment (follow-up permitted);
- Patient withdraws consent (termination of treatment and follow-up);
- Patient is unable to comply with protocol requirements;
- Patient demonstrates disease progression (unless continued treatment with study drug is deemed appropriate at the discretion of the investigator);
- Patient experiences toxicity that makes continuation in the protocol unsafe;
- Treating physician judges continuation on the study would not be in the patient's best interest:
- Patient becomes pregnant (pregnancy to be reported along same timelines as a serious adverse event);
- Lost to follow-up. If a research subject cannot be contacted despite repeated attempts during the 6 month period they will be considered lost to follow-up. All attempts to contact the subject during the 6 months must be documented and approved by the Data Monitoring Committee.

8.0 Outcome Measures

8.1 Improvement in FOG

8.1.1 Motor assessments

Giladi freezing of gait questionnaire (FOG-Q): Validated questionnaire with 6 items rated 0-4 for a total of 24 points in total. We will be looking for a 10% change in this questionnaire to suggest a subjective improvement in freezing of gait over the course of the study.

UPDRS Part III motor score: Validated rating scale used to quantify the movement disorders motor examination including items for bradykinesia, tremor, rigidity and gait.

Gait and balance measures: Will evaluate for changes in steady state gait and balance measures using the assessments outlined in section 7.2 including mean and percent coefficient of variability in:

Stride length

² Self-assessment questionnaires

PI: [name], PhD

Sponsor: UAMS

- Stride width
- Stride velocity
- Step time
- Step length
- Gait cycle time
- Swing cycle percent
- Stance cycle percent
- Single support percent
- Total double support percent
- Velocity
- Cadence
- Ambulation time

8.1.2 Cognitive assessments:

The following cognitive assessments will be administered by [name] or other trained study personnel. [name] (licensed psychologist) will supervise the interpretation of these results.

Montreal cognitive assessment (MoCA): commonly used scale to screen for cognitive dysfunction in Parkinson disease patients.

Frontal assessment battery (FAB): commonly used scale to screen for frontal lobe dysfunction that can be suggestive of atypical parkinsonisms and also associated with frontal gait disorders that also have FOG.

SCOPA-cog: cognitive rating scale used in European trials to track cognitive function in Parkinson disease patients.

Stroop test: test of mental flexability and set shifting using colored words that FOG patients have been shown in some preliminary studies to have more difficulty with than PD without FOG patients.

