3.3 Rationale

FOG is present in approximately 60% of patients with PD and is a major cause of gait impairment leading to falls, and the morbidity and decreased quality of life. Currently, other than levodopa therapy, which can be limited in later stages of disease when FOG occurs by dose dependent side effects, no alternative treatments exist. Modafinil, as described above, has been shown by the [name] lab to modulate pathways in the PPN that link arousal and gait dynamics. Additionally, PPN DBS has also been shown to modulate gait and falls in patients. As such, we propose to study whether Modafinil can improve FOG in PD. For this pilot study, we will focus on recruiting PD patients with FOG and use a delayed start trial model to determine whether FOG improves compared to placebo. We chose the delayed start trial model as opposed to just having a placebo arm as it will likely help with recruitment and subject retention if all subjects know that at least during 3 months of the trial they will all be receiving active drug. Additionally, preliminary data (unpublished, UAMS IRB#203234) from my lab suggests that PD patients with FOG have a faster rate of decline in objective gait parameters compared to PD patients, even over a period of 3-6 months. Therefore, with the delayed start model we will also determine if there are any changes in the slope of decline in PD-FOG patients over the period of the trial.

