4.1 Primary Objectives

- **4.1.1** To determine if 50 mg/day Modafinil decreases FOG in PD patients with FOG compared with placebo as measured by the Giladi Freezing of gait questionnaire (FOG-Q).
- **4.1.2** To determine if 50 mg/day Modafinil decreased the decline stride length seen in PD patients with FOG.

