4.4 Endpoints

4.4.1 Primary Endpoints

- 4.4.1.1 To determine if 50 mg/day Modafinil decreases freezing of gait in PD patients with FOG compared with placebo as measured by the Giladi Freezing of gait questionnaire (FOG-Q) after 12 weeks of active treatment or placebo. Subjects who drop out of the study after at least 6 weeks of either treatment arm will be included in this analysis.
- 4.4.1.2 To determine if 50 mg/day Modafinil decreased the decline stride length seen in PD patients with FOG. The rate of decline in stride length will be compared plotting the stride length at steady state in subjects in the early and late-start arms to determine if the rate of decline improves in subjects taking Modafinil in the early-start arm and whether this rate of decline also improves in the second phase of the trial in the delayed-start arm.

We will also determine if at the completion of 24 weeks, the early-start arm has differential change in slope of other continuous gait parameters (stride width, gait cycle time, gait cycle velocity, swing and stance percent, total single and double support time, cadence) compared to the delayed start arm suggesting that Modafinil slows the progression of the gait decline.

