6.2 Treatment Dosage and Administration

The research pharmacy will create a randomization log, randomizing 20 subjects 1:1 to early start or delayed start modafinil (Figure 1). Subjects will be assigned the next line in the log in order of treatment. Subjects in the early-start arm will receive Modafinil 50 mg oral daily (a.m.) for 24 weeks while subjects in the delayed-start arm will receive oral placebo for the first 12 weeks of active treatment followed by Modafinil 50 mg oral daily for weeks 13-24 of the active treatment period. The drug will be washed out for a 2 week period with repeat assessments to determine any withdrawal symptoms.

[figure not shown]

Figure 1: Delayed-start trial model with 1:1 randomization into an early-start arm with 10 subjects receiving Modafinil 50 mg oral daily for 24 weeks and 10 subjects randomized to a delayed-start arm receiving placebo for the 1st 12 weeks followed by Modafinil 50mg oral daily for weeks 13-24. Visits will be performed at initiation and randomization, followed by 6, 12, 18 and 24 week visits in the active phase with the final visit performed after a 2 week drug washout phase.

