10.0 STATISTICAL CONSIDERATIONS

The study is a prospective repeated measures longitudinal design. The primary outcome response is the FOG-Q total score and the stride length changes, and the secondary responses are the UPDRS Part III subscale, the PDQ-39, the RBD scale, and the Epworth Sleepiness Scale. These measures will be observed at 6 time points for both study arms. A primary statistical goal is to estimate the mean response at all six time points for each group and subsequently estimate changes in the outcome measures for each study group from baseline. Additionally, it is of interest to estimate the how the study groups differ in their mean change from baseline. A two group repeated measures linear model will be employed to determine significance for within each group and then to compare among the groups. Significance will be declared at the 5% level of significance and Bonferroni methods will be used for multiple comparisons. This analysis approach will be applied to the primary and secondary responses.

The study calls for 10 subjects in both arms for a total of 20 patients. Within a study arm the linear model will have in excess of 80% power to detect a 1.75 unit difference in observed means. Based on standard deviation estimates from previous researchers in similar settings,²² the FOGQ (the primary response) has a standard deviation of 3.58. This implies that we will have power to detect a 6.265 (1.75*3.58) unit difference among time point means at the 5% level of significance. Power calculations are from 'Tables of Sample Sizes in the Analysis of Variance' published by Bratcher.²³

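### Nothing in the plan makes the week-12 placebo comparison decide FOG-Q efficacy, so an uncontrolled 10% or within-arm improvement could be reported as benefit

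*Combined protocol and SAP*

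**What the plan says.** Section 4.1.1 asks whether modafinil reduces freezing compared with placebo. Section 4.4.1.1 fixes the time point: "as measured by the Giladi Freezing of gait questionnaire (FOG-Q) after 12 weeks of active treatment or placebo".

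Section 8.1.1 describes the scale as "Validated questionnaire with 6 items rated 0-4 for a total of 24 points in total" and then gives the only numeric threshold for improvement: "We will be looking for a 10% change in this questionnaire to suggest a subjective improvement in freezing of gait over the course", meaning the whole trial. It does not say whether the 10% refers to a patient's own baseline or to the 24-point scale, to single patients or arm means, at which visit, or against which arm.

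Section 10 names the estimation of each group's means and changes from baseline as a primary statistical goal. The difference between groups is added as a further matter of interest. For testing, "A two group repeated measures linear model will be employed to determine significance for within each group and then to compare among the groups". The 5% level and Bonferroni methods apply. Power is stated only within an arm.

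Entry requires a FOG-Q above 8 (Section 5.1). The schedule in Section 7.3 labels Visit 1 the screening visit and places the next FOG-Q at week 6. The legend to Figure 1 agrees: "Visits will be performed at initiation and randomization, followed by 6, 12, 18 and 24 week visits in the active phase". Both arms take modafinil in weeks 13-24 (Sections 4.0 and 6.2).

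**The concern.** The question in Section 4 is controlled. The threshold in Section 8.1.1, the first tests in Section 10 and the power statement are not. A change over the whole study includes 12 weeks with no placebo arm. A within-arm change, even at week 12, mixes any drug effect with placebo response, chance variation and regression to the mean, because the score that qualifies a patient is also the only scheduled pre-treatment score. Expectation may add to this. Section 3.3 counts on recruitment being easier if "all subjects know that at least during 3 months of the trial they will all be receiving active drug", and Section 8.1.1 itself calls the outcome a subjective improvement.

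No sentence says that the between-arm contrast decides efficacy. If both arms improved alike, a report could follow the plan and still present improvement in freezing as a benefit of modafinil.

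**Working it through.** **Inputs from the documents.** FOG-Q range 0-24, entry score above 8, SD 3.58, 10 patients per arm, six time points, 5% level with Bonferroni.

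**Assumptions, because the documents are silent.** Test-retest correlation ρ from 0.6 to 0.9; mean FOG-Q of the source population before selection, μ, from 10 to 14; placebo response of 0, 1 or 2 points; two-sided tests; Bonferroni over the five post-baseline visits.

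**1. The plan's own figure.** For a one-way ANOVA with k = 6, n = 10 and a standardized difference τ = 1.75, the noncentrality is nτ²/2 = 10 × 1.75²/2 = 15.3. The noncentral F with 5 and 54 df gives 83.3% power (82.5% with 45 error df). The difference in points is 1.75 × 3.58 = 6.265. The claim of more than 80% is reproduced, but it concerns time points within one arm.

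**2. What 10% could mean.** At the lowest qualifying score of 9, 10% of own baseline is 0.10 × 9 = 0.9 point. On the full scale it is 0.10 × 24 = 2.4 points, which is 2.4/3.58 = 0.67 SD and 2.4/6.265 = 0.38 of the difference in the power statement.

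**3. Regression to the mean.** The expected fall is (1 − ρ) × (mean qualifying score − μ). Keeping integer scores above 8 gives mean qualifying scores of 12.0, 13.1 and 14.5 for μ = 10, 12 and 14.
- Largest: (1 − 0.6) × (12.0 − 10) = 0.80 point.
- Smallest: (1 − 0.9) × (14.5 − 14) = 0.05 point.

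**4. How often the uncontrolled criteria are met with no drug effect.** Pairs of scores (SD 3.58, rounded, limited to 0-24, first score above 8) were simulated, with the placebo response subtracted from the second score. Ranges run over all ρ and μ and refer to one later visit.

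| Event | No placebo response | 1 point | 2 points |
|---|---|---|---|
| Single patient falls ≥ 10% of own baseline | 20-45% | 41-58% | 60-74% |
| Single patient falls ≥ 2.4 points | 6-29% | 18-41% | 39-54% |
| Arm mean (n = 10) falls ≥ 10% of baseline | 0-34% | 22-74% | 78-98% |
| Arm mean falls ≥ 2.4 points | 0-5% | 1-29% | 28-68% |
| Within-arm improvement significant, unadjusted (nominal 2.5%) | 3-11% | 19-55% | 50-97% |
| The same, Bonferroni for 5 visits (nominal 0.5%) | 0.7-2.9% | 6-27% | 22-82% |

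Hand check at μ = 10, ρ = 0.6. The SD of the later score given baseline is 3.58 × √(1 − 0.36) = 2.86, so the arm mean has SE 2.86/√10 = 0.91. The threshold is 0.10 × 12.0 = 1.2 points. With no placebo response, z = (1.2 − 0.8)/0.91 = 0.44, a probability of 0.33 (simulated 0.34). With 1 point, z = (1.2 − 1.8)/0.91 = −0.66, a probability of 0.75 (simulated 0.74).

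**5. The between-arm contrast.** With ρ = 0.8, μ = 12 and a 2-point placebo response in both arms, the two-arm comparison gives 5.1% false positives. Selection and a shared placebo response do not bias it.

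Its precision is limited. With 10 per arm and 3.58 as the SD of the quantity compared, power for 2.4 points is 29%. The smallest difference with 80% power is 4.74 points, and 80% power for 2.4 points needs about 2 × (1.96 + 0.84)² × 3.58²/2.4² ≈ 35 per arm. Baseline adjustment, with SD 3.58 × √(1 − ρ²), raises power for 2.4 points to 37% at ρ = 0.5 and 90% at ρ = 0.9.

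**The case against.** The strongest reply is that the plan already asks the right question. Section 4.4.1.1 sets the placebo comparison at week 12, and Section 10 goes on to compare the groups. A reader might infer that the plan defines success as a 10% change or as within-arm significance. It does not: the 10% sentence stands in a list of instruments, says only that such a change would suggest improvement, and is tied to no test. This stands, and it limits the point to what the plan leaves open.

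A reader might also infer that selection on a noisy score would by itself make an inert capsule look effective. The figures do not support that. Regression to the mean is 0.05-0.8 point, and without a placebo response the Bonferroni-corrected within-arm test is positive in at most about 3% of trials per visit. Entry also requires freezing on a neurologist's objective assessment and three months of stable therapy, which the simulation ignores. The high rates need an assumed placebo response.

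Three smaller replies also stand. The schedule marks FOG-Q as performed by staff, so it is not a pure self-assessment form. Section 3.3 does not say that subjects know which months are active, and the trial is double-blind. In a pilot, estimating within-arm change is reasonable. None of this supplies the missing statement of which contrast supports an efficacy conclusion.

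**Conclusion.** The concern holds in a limited form. The endpoint is controlled, but the only numeric threshold is undefined and uncontrolled, the tests begin within arms, and the only power statement is within an arm. An uncontrolled change could therefore be reported as efficacy without departing from the plan.

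The size of the risk rests on assumptions outside the documents. Placebo response is the main driver: with 1 point, an arm mean reaches 10% of its baseline in roughly a quarter to three quarters of trials with no drug effect. The base matters almost as much, since on the 2.4-point reading the same scenario gives 1-29%. The documents do not support a finding that the stated power is wrong or that the between-arm comparison is biased. This should be corrected, but it does not invalidate the design.

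**What to change.** In Section 10, state that FOG-Q efficacy is concluded only from the modafinil-minus-placebo difference in change from Visit 1 to Visit 3 (week 12), reported with its confidence interval. Add that within-arm changes, and all FOG-Q changes after week 12, are descriptive.

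In Section 8.1.1, state whether 10% means a patient's own baseline or the 24-point scale (2.4 points). Use it only as a reference for interpreting the week-12 between-arm difference, not as a stand-alone sign of improvement or a pass/fail margin.

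The cost is a few sentences and no new data. Within-arm improvement can no longer be claimed as efficacy. The decisive contrast will also be imprecise: unadjusted, with SD 3.58, the 95% confidence interval extends about 2.10 × 3.58 × √(2/10) = 3.4 points either side. That is a reason to present the result as an estimate, and not a reason to fall back on within-arm tests.
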